6 DEMOGRAPHICS AND OTHER BASELINE CHARACTERISTICS

6.1 Demographics

A by-study participant listing of Baseline demographics will be presented by treatment group for the ES. This will include the year of birth (if available), age (in years), gender, race, ethnicity,

height (in cm), weight (in kg) and body mass index (BMI), region and country. The age will be directly entered into the study database and will not be re-calculated for the statistical analysis.

Childbearing potential will be listed for the ES.

All demographic characteristics, except date of birth, obtained at the Screening visit or at Visit 2 in case of missing values will be summarized for the SS.

Body mass index in kg/m^2 is calculated based on the height (in m) and the weight (in kg) measured either at the Screening visit (Visit 1) or baseline visit (Visit 2) of CIDP04 using the following formula:

$$\text{BMI } (\text{kg}/\text{m}^2) = \text{weight } (\text{kg}) / [\text{height } (\text{m})]^2.$$

The BMI will be rounded to 1 decimal place.

Age will be classified into categories based on requirements for European Union Drug Regulating Authorities Clinical Trials (EudraCT) and clinicaltrials.gov reporting.

For the EudraCT reporting, the age categories will include:

- 18 to <65 years
- 65 to <85 years
- ≥ 85 years

For the clinicaltrials.gov reporting, the age categories will include:

- ≤ 18 years
- 19 to <65 years
- ≥ 65 years

Body weight at screening or Visit 2 of CIDP04 will be summarized in the following categories:

- <50 kg
- 50 to <70 kg
- 70 to <100 kg
- ≥ 100 kg

6.2 Other Baseline characteristics

The prior Ig treatments taken four months before the Baseline visit in CIDP04 will be listed for the SS by treatment group for all study participants and will include the reported term, preferred term (PT), dose, route of administration, frequency, formulation, start/stop dates and duration (in days) and if it was a rescue treatment in the parent study or not. For definition of prior treatments see [Section 6.4.1](#).

Duration will be calculated as follows:

$$\text{Duration (in days)} = (\text{End date of Ig treatment} - \text{Start date of Ig treatment}) + 1$$

In addition, the following variables will be listed and summarized at baseline for the SS by treatment group:

- iRODS score (raw sum score, logit locations and centile metric scores)
- INCAT
- Grip strength (assessed by site personnel and patient reported grip strength)
- Immunological variables (IgG [including total IgG and IgG subclasses], IgM, IgA, IgE)
- Cytokines
- Serum (C3 and C4) and plasma complement levels (C3a and C5a)

6.3 Medical and procedures history

Medical history updates, not reported in CIDP01, will be listed for the SS by treatment group and will include the MedDRA system organ class (SOC), high level term (HLT) and preferred term (PT).

Procedure history updates (not reported in CIDP01) and concomitant medical procedures will be listed based on the SS.

6.4 Prior and concomitant medications

Prior and concomitant medications will be listed for the SS by treatment group and for all study participants and will include the WHODD Anatomical Main Group [Level 1], Therapeutic Subgroup [Level 2], PT and reported term. The listing will also include the dose per intake and unit, frequency, formulation, route of administration, indication, category (prior and concomitant, prior, or concomitant) and both start and end date (or ongoing, if applicable).

6.4.1 Prior medication definition

Prior medications will include any medications that started prior to the first administration of IMP for study participants with a gap period between the study CIDP01 and CIDP04. This includes any medications that started and stopped prior to dosing in CIDP04 as well as those which started prior to dosing and continued after (classified as prior and concomitant medications) if a gap period was present. For study participants who entered the study on the last visit day of CIDP01 prior medications will not be defined.

6.4.2 Concomitant medication definition

Concomitant medications will include any medication that has been taken at least once (on or after the first administration of IMP of CIDP04 study) during the Treatment Period and/or the Observation Period.

Any medication that started prior to the first administration of IMP and continued after dosing will be classified as prior and concomitant. Any medication that started on or after the first administration of IMP will be classified as concomitant only.

Any medications with missing dates and/or times will be handled as described in [Section 4.2.7](#) in order to classify them as prior or concomitant.

The following rules will be used to assign concomitant medications to the study periods:

- Treatment Period: a medication will be assigned to Treatment Period if it has been taken at least once between the first administration of IMP until Visit 26/PEOT (non-inclusively).

This includes medications that started prior to the first IMP and continued during Treatment Period.

- Observation Period: a medication will be assigned to Observation Period if it has been taken at least once between Visit 26/PEOT (inclusively) and the FV. This includes medications that started prior to the Observation Period.

Medications taken during both study period will be listed once, but the study period will indicate both study periods.

7 MEASUREMENTS OF TREATMENT COMPLIANCE

The study medication will be administered and monitored by the investigator or designee. Any dosing deviations (eg, incomplete infusion volume administered, infusion temporarily interrupted, infusion discontinued) will be discussed at the DEM and any actions taken regarding the analyses will be documented accordingly and discussed in the CSR.

All drug administration details (including exposure category described in [Section 10.1](#), date, start and stop time of infusion, interruptions, discontinuations, total planned volume and actual volume delivered, planned and actual infusion rates (where applicable), location of infusion site) will be listed. The reasons for any interruptions or discontinuations will be included in the listing. The duration of the infusion, in minutes, and compliance will also be calculated and presented.

Compliance, percent of planned dose administered, will be calculated based on the planned and actual volume delivered as follows:

$$\text{Percent of Planned dose administered} = (\text{Total actual volume delivered (mL})/\text{Total planned volume (mL)}) * 100.$$

Actual volume delivered and total planned volume (ie, according to Section 7.2 of protocol) will be captured in the eCRF. In case of interruption the sum of actual volumes delivered, and the total planned volume recorded into the eCRF will be used for the calculation.

There will be no specific analysis of compliance.

8 EFFICACY ANALYSES

All summaries of efficacy data will be performed on the FAS. Additional outputs are repeated for the MFAS where indicated. Listings will be based on the SS. Treatment group assignment for efficacy data presentation will be according to the actual treatment regimen.

8.1 iRODS

8.1.1 iRODS scores

The iRODS is a linearly weighted patient-reported outcome measure (questionnaire) that specifically captures activity and social participation limitations in patients with CIDP. The iRODS scale was constructed based on the World Health Organization (WHO) International Classification of Functioning, Disability and Health, literature search, and patient interviews.

All 24 items of iRODS meet Rasch model expectations. The questionnaire consists of 24 items (including eating, taking a shower, walking a flight of stairs, standing for hours, etc.) and assesses a patient's perception of their ability to perform daily and social activities. Patients have

3 response options: 0=impossible to perform; 1=performed with difficulty; and 2=easily performed, performed without difficulty.

The raw sum scores of iRODS (range 0 to 48) is an ordinal scale and does not allow for easy interpretation of differences. For this reason, the ordinal scale will be translated to log odds units (logits) scale using the nomogram in [Section 13.1](#), placing patients' estimates on the same logit scale. The primary analysis and iRODS summary will be performed on logit locations. For easier interpretation the person locations (logits) will be translated to centile metric scores changing from 0 (most severe activity and social participation restrictions) to 100 (no activity and social participation limitations).

Both transformed and untransformed data will be listed and summarized by treatment group for each scheduled assessment during the Treatment and Observation Period.

The individual items of the iRODS and overall score will be listed by treatment group and timepoint using the SS. Overall scores will be displayed including raw sum score, logit locations and centile metric scores as well as changes from Baseline in raw sum score, logit locations and centile metric scores. Descriptive summaries will be presented by treatment group and timepoint for both absolute values and changes from Baseline based on the FAS. Raw sum score summary will show only n, median, minimum, maximum. In addition, frequencies of raw scores by each iRODS questionnaire item (eating, taking a shower, walking a flight of stairs, standing for hours, etc.) will be calculated.

Mean change from Baseline including 90% CI of the centile metric score will be plotted against timepoint for both treatments.

The summary tables will be repeated based on the MFAS.

8.2 Adjusted INCAT

8.2.1 Adjusted INCAT score

The INCAT disability scale is a 10-point clinician-reported ordinal measure capturing problems in daily arm and leg activities and mobility. The measure captures daily activities such as dressing the upper part of the body, doing and undoing buttons and zips, washing and brushing hair, and handling coins. Each item is scored as being “not affected”, “affected but not prevented”, or “prevented”. The leg scale measures problems with walking, considering the use of aids.

The investigator (or qualified personnel) will record the participants’ INCAT arm and leg disability score at each scheduled assessment.

The INCAT score is the sum of the eCRF-captured arm disability classification (from 0 to 5) and leg disability classification (from 0 to 5). The INCAT scale ranges from 0 (no signs of disability) to 10 (most severe disability score).

If there is only one point deterioration/improvement in the participant upper limb score (arm disability score), ie, from 0 (normal) to 1 (minor symptoms) or from 1 to 0, this difference should not be considered as a significant worsening/improvement and the related difference between baseline and the respective visit should be ignored when evaluating the adjusted INCAT score for the visit in the following way:

For each visit's INCAT score, the adjusted INCAT is

- a. adjusted INCAT score = INCAT score - 1, if the arm disability score for this participant is 0 at baseline and 1 at the respective visit
- b. adjusted INCAT score = INCAT score +1, if the arm disability score for this participant is 1 at baseline and 0 at the respective visit
- c. adjusted INCAT score = INCAT score in any other case.

	Baseline score	Visit score	Total adjusted INCAT score
Arm disability score	0	1	Total adjusted INCAT score = Total visit INCAT score – 1
	1	0	Total adjusted INCAT score = Total visit INCAT score + 1
	Any other case		No adjustment

Raw and adjusted INCAT scores will be listed. Adjusted INCAT scores will be summarized by treatment group for each scheduled assessment during the Treatment and Observation Period together with changes from baseline.

Mean change from Baseline in adjusted INCAT score, including 90% CI will be plotted against timepoint for both treatments.

8.2.2 CIDP relapse (INCAT)

CIDP relapse (adjusted INCAT) is defined as an increase from Baseline of at least 1 point in the adjusted INCAT score.

The statistical methods and presentations applied to CIDP relapse (adjusted INCAT) and time to CIDP relapse (adjusted INCAT) will be the same as for CIDP relapse and time to CIDP relapse (iRODS), see Section 8.1.2.

8.3 Maximum Grip Strength (Assessed by Site Personnel)

8.3.1 Maximum Grip Strength (Assessed by Site Personnel)

Grip strength is assessed by qualified site personnel at each scheduled assessment. Qualified site personnel will be trained regarding obtaining and recording measurements. At each scheduled visit, the grip strength, generated by the participant, and measured using a standardized tool, will be evaluated 3 times in the dominant hand. All 3 assessments will be recorded in the eCRF and listed. For analyses, UCB will utilize the maximum of the 3 assessments, which will be flagged in listings.

Maximum grip strength as assessed by site personnel will be listed and summarized by treatment group for each scheduled assessment during the Treatment and Observation Period together with changes from baseline.

8.3.2 CIDP relapse (Maximum Grip Strength, 14 kPa)

CIDP relapse (maximum grip strength as assessed by site personnel, 14 kPa) is defined as a clinically important deterioration from Baseline in grip strength as measured by site personnel, ie, a decline of >14kPa.

The statistical methods and presentations applied to CIDP relapse (Maximum Grip Strength, 14 kPa) and time to CIDP relapse (Maximum Grip Strength, 14 kPa) will be the same as for CIDP relapse and time to CIDP relapse (iRODS), see Section 8.1.2.

8.3.3 CIDP relapse (Maximum Grip Strength, 8 kPa)

CIDP relapse (maximum grip strength as assessed by site personnel, 8 kPa) is defined as a clinically important deterioration from Baseline in grip strength as measured by site personnel, ie, a decline of >8 kPa.

The statistical methods and presentations applied to CIDP relapse (Maximum Grip Strength, 8 kPa) and time to CIDP relapse (Maximum Grip Strength, 8 kPa) will be the same as for CIDP relapse and time to CIDP relapse (iRODS), see Section 8.1.2.

8.4 CIDP Relapse

The event of CIDP relapse is defined by first occurrence of either relapse across the 3 calculated criteria: iRODS relapse, adjusted INCAT relapse and maximum grip strength as assessed by site personnel (14 kPa) relapse as defined in sections 8.1.2, 8.2.2 and 8.3.2 and "other" as captured in the eCRF by the investigator. It will be described and analyzed in the same way as the individual relapse definitions.

The specified reason for "other" relapse will be included in the listing of CIDP relapse.

A listing will present if a participant experienced a CIDP relapse, CIDP relapse (iRODS), CIDP relapse (INCAT), CIDP relapse (Maximum Grip Strength, 14 kPa), CIDP relapse (Maximum Grip Strength, 8 kPa) or any other relapse reported by the investigator.

8.5 Use of rescue medication

The percentage of participants with concomitant medication identified as rescue medication [Yes/No] in the eCRF and time to first rescue medication administration will be summarized by treatment group and for all participants and listed by treatment group at each scheduled assessment during the Treatment and Observation Period.

If a participant receives rescue medication at multiple times, the relative day of the first occurrence is used to define the time to rescue medication.

The statistical methods applied to use of rescue medication and time to use of rescue medication will be the same as for CIDP relapse (iRODS) summary tables.

8.6 RT-MRC sum score

The RT-MRC sum score is a summation of the RT-MRC grades in integers of the following muscles on each side: upper arm abductors, elbow flexors, wrist extensors, hip flexors, knee extensors, and foot dorsal flexors.

The RT-MRC sum score was developed based on a Rasch analysis of the original MRC grading system ([Me10]; [Me02]; [Va12]). The original MRC sum score grades from 0 to 5 (0 = No movement, no contraction; 1 = Visible contraction without movement; 2 = Movement, but only with gravity eliminated; 3 = Movement against gravity; 4 = Movement against resistance, but weaker than normal; 5 = Normal Strength). The MRC grades were rescored from 6 to 4 response options (0, paralysis; 1, severe weakness; 2, slight weakness; 3, normal strength) for the RT-MRC in order to acceptably fulfill Rasch model expectations. Sum scores range from 36 "normal" to 0 "quadriplegic".

Values and changes from Baseline in original MRC sum score and in RT-MRC sum score will be summarized by treatment group and for all participants and listed by treatment group at each scheduled assessment during the Treatment and Observation Period.

8.6.1 CIDP PRO and Fatigue scale

The CIDP PRO instrument consists of 2 domain scales:

- Pain Severity numeric rating scale

- Neuropathy scale.

Pain Severity consisting of 4 items assessing pain severity in the past 7 days and at the time of completion of the instrument, using 0-10 numeric rating scales. Summed total raw score will range between 0 to 40 with higher scores reflecting higher levels of pain severity.

The Neuropathy scale consists of 17 items rated within a 7-day recall period on a 6-point Likert severity scale ranging from “none” to “very severe”. The summed total raw score will range from 17 to 102 with higher scores reflecting higher levels of pain and physical sensations severity.

The **Fatigue instrument** consists of 3 domain scales; Physical Fatigue comprising 16 items; Mental Fatigue comprising 18 items and Fatigability comprising 21 items. All 55 items across the 3 domain scales are rated within a 7-day recall period on a 5-point Likert frequency scale ranging from “none of the time” to “all of the time”. The summed total raw scores for each of the 3 scales will range between 16 and 80; 18 to 90 and 21 to 105 points for the Physical, Mental, and Fatigability, scales respectively with a potential for an exploratory total overall score ranging from 55 to 275. Higher scores reflect higher levels of fatigue across all domain scale scores.

Values and changes from Baseline in CIDP-PRO instrument and in fatigue scores will be listed by treatment group at each scheduled assessment during the Treatment and Observation Period.

Summary tables will be provided at an item level. If items are missing, the sum will be set to missing.

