3.3 Exploratory objectives

The exploratory objectives of the study are to assess the PD, PK, and immunological variables in the treatment course with rozanolixizumab and to assess whether long-term dosing of rozanolixizumab improves PROs. These include:

- The PD effect of rozanolixizumab as measured by the total IgG concentrations in serum

- The effects of rozanolixizumab on the concentrations of total protein, albumin, α - and β -globulins, IgG subclasses, IgM, IgA, IgE, and serum and plasma complement levels
- The incidence and emergence of ADA with respect to immunogenicity and PK and PD
- The effect of rozanolixizumab on complement and cytokines
- The plasma concentrations of rozanolixizumab administered by sc infusion
- The PD effect of rozanolixizumab as measured by NF-L in serum
- The effect of rozanolixizumab on CIDP-specific auto-antibody levels
- The effect of rozanolixizumab on vaccine antibody levels (influenza A and tetanus)
- The effect of rozanolixizumab on exploratory biomarkers, and explore the relationship between protein and metabolite biomarkers and cause, progression, and appropriate treatment of CIDP

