2.1.3 Exploratory objectives

The exploratory objectives of the study are to assess the PD, PK, and immunological variables in the treatment course with rozanolixizumab and to assess whether long-term dosing of rozanolixizumab improves patient-reported outcomes (PROs). These include:

- The PD effect of rozanolixizumab as measured by the total immunoglobulin G (IgG) concentrations in serum
- The effects of rozanolixizumab on the concentrations of total protein, albumin, α - and β globulins, IgG subclasses, immunoglobulin M (IgM), immunoglobulin A (IgA), immunoglobulin E (IgE), and serum and plasma complement levels
- The incidence and emergence of anti-drug antibody (ADA) with respect to immunogenicity and PK and PD

- The effect of rozanolixizumab on complement and cytokines
- The plasma concentrations of rozanolixizumab administered by subcutaneous (sc) infusion
- The PD effect of rozanolixizumab as measured by neurofilament light chain (NF-L) in serum
- The effect of rozanolixizumab on CIDP-specific auto-antibody levels
- The effect of rozanolixizumab on vaccine antibody levels (influenza A and tetanus)
- The effect of rozanolixizumab on exploratory biomarkers, and explore the relationship between protein and metabolite biomarkers and cause, progression, and appropriate treatment of CIDP

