2.2.2.2 Patient-reported outcome variables

- Values and change from Baseline in fatigue domain scores at each scheduled assessment during the Treatment and Observation Periods
- Values and change from Baseline in CIDP patient-reported outcome (PRO) instrument domain scores at each scheduled assessment during the Treatment and Observation Periods
- Values and change from Baseline in Patient Global Impressions of Severity (PGIS) at each scheduled assessment during the Treatment and Observation Periods
- Patient Global Impressions of Change (PGIC) value at each scheduled assessment during the Treatment and Observations Periods

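### The CIDP PRO and fatigue variables are domain scores, but SAP 8.6.1 names summary tables only at item level, and SAP 3.9 does not declare this or the missing 0 to 100 scoring

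*SAP*

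**What the plan says.** One exploratory objective (Protocol 3.3, repeated in SAP 2.1.3) is "to assess whether long-term dosing of rozanolixizumab improves PROs". The variables are set at domain level. For fatigue, SAP 2.2.2.2 has "Values and change from Baseline in fatigue domain scores at each scheduled assessment during the Treatment and Observation Periods"; for the other instrument, "Values and change from Baseline in CIDP patient-reported outcome (PRO) instrument domain scores at each scheduled assessment". Protocol 4.2.2 defines them the same way.

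SAP 8.6.1 describes two CIDP PRO domains (Pain Severity, Neuropathy) and three fatigue domains (Physical, Mental, Fatigability), with raw-sum ranges. It then specifies three things:

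- Listings: "Values and changes from Baseline in CIDP-PRO instrument and in fatigue scores will be listed by treatment group at each scheduled assessment".
- Tables: "Summary tables will be provided at an item level".
- Missing items: "If items are missing, the sum will be set to missing".

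Protocol 10.4.1 and 10.4.2 also say that, once the scales have been refined with CIDP01 data, each domain will be scored on a transformed 0 to 100 interval scale. SAP 8.6.1 does not mention that scoring. SAP section 1 names 3.9 as the place where changes from the protocol are recorded, and 3.9 has no entry on CIDP PRO or fatigue.

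**The concern.** The scores that the plan defines as its variables are not the quantities it tabulates. A reader of the study report would get group-level tables for individual questions. To see how any of the five domains moved by visit, the reader would have to go through participant listings.

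Two things are at stake. First, the pre-specified variable has no pre-specified group summary. Second, with many item results and no order of importance among them, the text of the report could dwell on whichever items changed most. That second point is a general reporting risk, and nothing in the documents suggests that it is intended.

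**Working it through.** **1. Are the domain sums well defined?** SAP 8.6.1 gives item counts, response scales and ranges. The Likert codings (1 to 6 for Neuropathy, 1 to 5 for fatigue) are not stated and are assumed here. Range = items × lowest code to items × highest code.

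| Score | Items | Computed | Stated |
|---|---|---|---|
| Pain Severity | 4 | 4×0 to 4×10 = 0 to 40 | 0 to 40 |
| Neuropathy | 17 | 17×1 to 17×6 = 17 to 102 | 17 to 102 |
| Physical Fatigue | 16 | 16×1 to 16×5 = 16 to 80 | 16 to 80 |
| Mental Fatigue | 18 | 18×1 to 18×5 = 18 to 90 | 18 to 90 |
| Fatigability | 21 | 21×1 to 21×5 = 21 to 105 | 21 to 105 |
| Fatigue total (exploratory) | 55 | 55×1 to 55×5 = 55 to 275 | 55 to 275 |

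All six ranges reproduce. The sums are well defined, and the missing-item rule shows that the plan derives them.

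**2. What is tabulated?** Items: 4 + 17 + 16 + 18 + 21 = 76. Domain scores: 0 of 2 + 3 = 5. Protocol 8.2.5 and 8.2.9 place these PROs at five post-Baseline dosing visits in Part 1 (Weeks 5, 9, 13, 17 and 21). Per treatment group that gives 76 × 5 = 380 item-by-visit summaries, and none of the 5 × 5 = 25 domain-by-visit summaries.

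**3. Is the difference between listing and summarising deliberate wording?** The neighbouring RT-MRC section (SAP 8.6) provides both outputs: "Values and changes from Baseline in original MRC sum score and in RT-MRC sum score will be summarized by treatment group", and also listed. SAP 8.1.1 gives descriptive summaries of iRODS overall scores, 8.2.1 and 8.3.1 summarise adjusted INCAT and grip strength, and 8.6.2 tabulates PGIS and PGIC. Within SAP section 8, only CIDP PRO and fatigue have defined scores that are listed while the named tables stop at items.

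**4. Can item tables stand in for domain tables?** No. The median of a sum does not follow from item medians. The SD of a sum needs the covariances between items. For k items with equal SD s and common correlation ρ, SD of the sum = s × √(k + k(k−1)ρ). For illustration, let ρ run from 0 to 1:

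- Pain Severity, k = 4: from √4 = 2s to √(4 + 12) = 4s.
- Fatigability, k = 21: from √21 ≈ 4.6s to √(21 + 420) = 21s.

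The item tables do not show where in that span the truth lies. Item means may also rest on different participants from the sums, because one missing item voids the sum. If each item were independently missing with probability p, an assumption since the documents give no rate, the share of sums lost is 1 − (1 − p)^k. For p from 0.5% to 2% that is about 2% to 8% for Pain Severity and 10% to 35% for Fatigability.

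**The case against.** The strongest reply is that SAP 8.6.1 never says domain scores will not be summarised. SAP 3.1 has a general rule that continuous variables are summarised by group and visit. The missing-item rule sits directly after the sentence on tables and could be read as covering sums in tables. SAP section 1 keeps the protocol's analysis where the SAP is silent. Against this, 8.6.1 is not silent: it names the level of the tables, and a specific sentence prevails over a general one. At best the two texts conflict, and that also needs resolving.

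A second reply is that item-level output may have been chosen because both instruments were still to be refined with CIDP01 data, so raw sums over the full item set are provisional. SAP 8.1.1 itself cautions that differences in a raw ordinal sum are hard to interpret. This stands, and it shapes the fix. It is a reason for a modest format and for stating the choice, but it does not justify leaving the defined variables without any summary.

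A third is that Protocol section 14 prescribes no table for these scores, so item-level tables are not clearly a change that 3.9 had to record. This has some force. The undeclared departure is plainer for the 0 to 100 scoring, which the protocol promises and the SAP omits.

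A reader might also infer that the PRO objective cannot be answered at all. The documents do not support that. The objective speaks of PROs in general and not of domain scores, and iRODS, which is patient-reported, is summarised with change from Baseline. PGIS and PGIC cover both CIDP symptoms and fatigue and are tabulated. Nor are the data lost, since the scores and their changes are listed. Nor does the plan call for 76 separate tables, because one table could hold all items of a domain.

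**Conclusion.** The point holds for two instruments. As written, SAP 8.6.1 gives group-level tables for 76 items and for none of the 5 domain scores that the protocol and SAP define as the variables. SAP 3.9 records neither that choice nor the dropped 0 to 100 scoring. This rests on reading the specific sentence in 8.6.1 as governing over the general rule in SAP 3.1.

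The consequence is limited. The objective is exploratory, the study is a single-arm open-label extension, no test is planned on these scores, and the primary safety objective is untouched. Domain tables would describe change; without a concurrent control they could not show that treatment caused it. The change is still worth making, because the missing summaries are those of the defined variables and the raw sums are already derived.

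**What to change.** In SAP 8.6.1, add summaries of value and change from Baseline for the five raw domain sums, by treatment group and visit, and keep the item tables as supporting. Because the sums are ordinal and provisional, the summaries may follow the SAP's format for the iRODS raw sum: n, median, minimum and maximum. Showing n also reveals how many sums the missing-item rule removes.

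If the scoring derived from CIDP01 is available, add the 0 to 100 domain scores in the same layout. If it is not, record their omission in SAP 3.9 with the reason.

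The raw-sum part costs a few tables from sums the plan already derives. The 0 to 100 scores would need additional derivation, because the SAP does not contain the conversion.
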